After the individual has been screened and is determined to meet the inclusion and exclusion criteria they will be scheduled for two pre-treatment appointments and sent a consent form to review ahead of time. As part of the inclusion and exclusion criteria, the participant must have an appointment with their primary care provider or a hospital internist to complete a physical exam and required tests (EKG, CXR, CMP, CBC, and head CT scan). At the first pre-treatment appointment (Visit 1), the participant and their legal guardian will go over the consent form with the investigator. In addition to the consent form, to be signed by the legal guardian, the

participant will receive an assent of the cognitively impaired. After giving consent, the legal guardian will be given a Sentara release of medical information form so that investigators will have access to the ECT-performing physician's medical notes. The guardian or other caregiver will then fill out the ASD Diagnostic Checklist, Repetitive Behavior Scale- Revised, and the Aberrant Behavior Checklist. The physician will complete the Self-Injury Trauma Scale, which documents the number, type, and severity of unhealed self-injury traumas. At the end of the Visit 1, the guardian/ caregiver will receive a Subject Diary Card to record the number of self-injury episodes per day, the number of aggressive episodes per day, and the perceived severity of episodes that day. The Diary Card also has space to record the medication taken by the participant every day.

The second pre-treatment appointment (Visit 2) will consist of a complete psychiatric evaluation with review of all medical evaluations. The subject must receive medical clearance as defined by Sentara Norfolk General Hospital to undergo ECT treatment. The first Diary Card will be collected at this time, and a second Diary Card will be given.

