After acute ECT treatment is complete, patients and their guardians/ caregiver will return to EVMS Department of Psychiatry and Behavioral Sciences for post-treatment appointments (Visits 15-18). At these post-treatment appointment guardians/ caregiver will complete the ASD

Diagnostic Checklist, Repetitive Behavior Scale- Revised, and the Aberrant Behavior Checklist. The physician will complete a second Self-Injury Trauma Scale. At this time the Diary Card will be collected and subjects will receive Diary Cards for 1 month. Visits 15-18 will occur at 1 month, 2 months, 6 months, and 12 months post – acute ECT treatment. See the next page for a timeline summary of visits.

		Appointment Type	To-Do	Diary Card
Week 1	Visit 1	Pre- ECT Appointment	Consent and Assent forms, Release of Medical Information, ADC, RBS-R, ABC, Self-Injury Trauma Scale	Receive Diary Card 1
Week 2	Visit 2	Pre- ECT Appointment	Psychiatric Evaluation, Medical Clearance	Return DC 1, Receive DC 2
Week 3	Visit 3	ECT	Determine Seizure Threshold	Return DC 2; Receive DC 3
	Visit 4	ECT	Treatment	
	Visit 5	ECT	Treatment	
Week 4	Visit 6	ECT	Treatment	Return DC 3; Receive DC 4
	Visit 7	ECT	Treatment	
	Visit 8	ECT	Treatment	
Week 5	Visit 9	ECT	Treatment	Return DC 4; Receive DC 5
	Visit 10	ECT	Treatment	
	Visit 11	ECT	Treatment	
Week 6	Visit 12	ECT	Treatment	Return DC 5; Receive DC 6
	Visit 13	ECT	Treatment	
	Visit 14	ECT	Treatment	
Week 7	Visit 15	Post- ECT visit	ADC, RBS-R, ABC, Self-Injury Trauma Scale	Return DC 6; Receive DC 7, 8, 9, 10
Week 11	Visit 16	Post- ECT visit	ADC, RBS-R, ABC, Self-Injury Trauma Scale	Return DC 7, 8, 9, 10
6 Months	Visit 17	Follow-up visit	ADC, RBS-R, ABC, Self-Injury Trauma Scale	
12 Months	Visit 18	Follow-up visit	ADC, RBS-R, ABC, Self-Injury Trauma Scale	

Measures

Self-Injury Trauma Scale (SIT) allows differentiation and quantification of self-injury. In conjunction with a complete medical assessment, the physician records location of injury, type of injury, number of injuries, and an estimate of severity. Given these findings a Number Index, Severity Index, and Estimate of Current Risk can be calculated. The scale has been shown to have high interrater reliability.⁴

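### Does placing medical clearance at Visit 2, when it is also an entry criterion, make the enrolment sequence unworkable?

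*Protocol*

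**What the plan says.** The protocol's 'Inclusion and exclusion criteria' section requires every subject to be medically cleared under the existing clinical ECT protocol (EKG, chest X-ray, metabolic panel, blood count). It adds a head CT in a separate sentence and accepts results less than 6 months old. It also requires a psychiatric evaluation by the principal investigators. 'Study Design' says that a patient already enrolled for ECT who meets the criteria enters the study once consent or assent is given.

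The Procedure section then sets the order:

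- Booking: "After the individual has been screened and is determined to meet the inclusion and exclusion criteria they will be scheduled for two pre-treatment appointments".
- Tests: "As part of the inclusion and exclusion criteria, the participant must have an appointment with their primary care provider or a hospital internist". That appointment covers a physical examination and the five tests, head CT included.
- Consent: "At the first pre-treatment appointment (Visit 1), the participant and their legal guardian will go over the consent form with the investigator". The release form follows: "After giving consent, the legal guardian will be given a Sentara release of medical information form".
- Evaluation: "The second pre-treatment appointment (Visit 2) will consist of a complete psychiatric evaluation with review of all medical evaluations".
- Clearance, in the Visit 2 paragraph: "The subject must receive medical clearance as defined by Sentara Norfolk General Hospital to undergo ECT treatment".

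The visit table agrees with the last two items. Its entry for Week 2, Visit 2 reads "Psychiatric Evaluation, Medical Clearance". ECT starts at Visit 3, in Week 3.

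**The concern.** A criterion that must be satisfied before two visits are booked cannot also be decided at the second of them. Taken strictly, the sequence is circular for clearance, and seemingly for the psychiatric evaluation too.

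The second worry is consent. If the physical examination and five tests are entry criteria in that strict sense, all of them come before Visit 1, where the legal guardian consents for an adult who may not self-consent. 'Data Management' requires consent before any data collection and names laboratory values among the information collected. Study-required tests before consent, a head CT included, would be a serious matter.

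The third is the meaning of N=20. A patient who gives baseline scales at Visit 1 and is then not cleared at Visit 2 has no post-ECT value for the pre/post comparison in Aim 2. Each such patient is 1/20 = 5% of the planned sample.

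**Working it through.** The protocol states no figure on this point, so there is none to reproduce. The check sets the sections side by side.

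| Item | 'Inclusion and exclusion criteria' and opening of Procedure | Visit paragraphs and visit table |
|---|---|---|
| Medical clearance | Entry criterion, so before booking | Visit 2, Week 2 |
| Psychiatric evaluation | In the criteria paragraph | Visit 2, Week 2 |
| Physical examination and five tests | Part of the criteria, no date given | Reviewed at Visit 2 |
| Consent | Not placed | Visit 1, Week 1 |
| Baseline scales | Not placed | Visit 1, after consent |
| First ECT | Not placed | Visit 3, Week 3 |

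**Clearance.** The two columns conflict. This is the one clear inconsistency.

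**Psychiatric evaluation.** The criteria paragraph says the evaluation is to judge response to ECT as well as suitability for it, and that ASD symptoms are assessed before treatment, during it and at follow-up. Response and follow-up cannot be known at booking. The sentence describes study assessments that happen to sit in the criteria paragraph, so it is not cleanly a condition for booking.

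**Tests and consent.** The Procedure section requires an appointment with the patient's own primary care provider or an internist and gives no date for it. The only fixed point is that results must exist by Visit 2, when they are reviewed. The 6-month window allows tests done before any contact with the study, and 'Study Design' describes patients already enrolled for ECT. A result obtained in ordinary care becomes study data when the investigators collect it, and the review described is at Visit 2, after consent. The rule in 'Data Management' is therefore not contradicted. The release form covers the notes of the physician giving ECT, not these tests, so its timing does not bear on the question.

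**Size.** The protocol gives neither the share of candidates who already hold current results (s) nor the share not cleared at Visit 2 (f). With assumed values:

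- Needing at least one new test, 20 × (1 − s): s = 0, 0.5, 0.9 gives 20, 10, 2.
- Entered but not cleared, 20 × f: f = 0.05, 0.10, 0.20 gives 1, 2, 4, leaving 19, 18, 16 treated.
- Consents needed for 20 treated, 20/(1 − f): 21.1, 22.2, 25.0.

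These results only restate s and f. The first line does not say whether any new test falls before consent, because the tests have no stated date.

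**Order under the table.** Pre-screen and booking; consent and baseline scales (Visit 1); evaluation, review and clearance (Visit 2); ECT (Visit 3). Each step can be carried out, and none needs the result of a later one.

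**The case for a change.** The strongest case for a change is that the criterion is being cleared, not merely holding test results, and the table lists clearance itself at Visit 2. A site that followed the opening of the Procedure section to the letter could not comply. The staged sequence that would work is nowhere written out, and where an adult may not self-consent, the point of consent ought to be explicit.

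The head CT is the best part of this case. Both 'Inclusion and exclusion criteria' and 'Protection against Risks' name it apart from the clinical ECT protocol, so the ordinary-care explanation that fits the other four tests is not expressly given for it. That stands as an unclear point. It does not show that a scan is done for research before consent, because the 6-month window and the undated appointment apply to the scan as well.

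The N=20 argument is weaker. 'Study Design' ties entry to consent or assent, and how patients entered but untreated are analysed is commonly left to the statistical analysis plan, which is not at hand.

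A side point is that the Procedure section speaks of low risk while 'Protection against Risks' says that patients at increased risk will not be excluded. The two can be read together as clearance case by case. No view is taken here on the clinical rule.

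**Conclusion.** The protocol contains a wording slip: clearance is an entry criterion in one place and a Visit 2 step in another. No change to the plan is called for. The visit table supplies a workable order that a site would naturally follow, and following it alters no result, conclusion or safeguard. Consent still precedes the baseline scales, and clearance still precedes ECT.

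No documented figure moves. The loss of 1, 2 or 4 of 20 patients arises only under assumed non-clearance rates of 5%, 10% or 20%, and rewording the sequence would not alter those rates.

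The conclusion rests on two readings: that the table governs the order of visits, and that the tests are obtained in ordinary care or after consent. The text supports the first directly. It supports the second well for the four tests in the clinical ECT protocol and less firmly for the head CT.

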Use of Electroconvulsive Therapy to Treat Self-Injurious Behavior in Adults with Autism Spectrum Disorders

I. Overview:

Self-injurious behavior (SIB) is one of the strongest predictors of psychiatric hospitalization among children with Autism Spectrum Disorder (ASD) aged 5 to 21 years. While self-injury in some patients is operant-based, involuntary self-injury can be a presentation of catatonia. When psychopharmacologic interventions fail, electroconvulsive therapy (ECT) is a safe and highly effective alternative to treating catatonia and major depression. Given that catatonia may present as SIB, especially in patients with ASD, several case studies have used ECT to minimize the self-injury in treatment-resistant patients. This study will use formal measures, including the Aberrant Behavior Checklist (ABC), Repetitive Behavior Scale (RBS), and the Self-Injury Trauma (SIT) Scale to monitor the outcome of using ECT to treat SIB in patients with ASD, for whom psychotropic medication has not worked. This study will be fundamentally different from the previously published literature on the subject in that this will be a prospective study which will aim to recruit multiple participants in an open label study.

II. Specific Aims and Hypotheses:

SIB in ASD is both physically and emotionally damaging to patients. Many patients with SIB who have ASD are treatment resistant in regard to psychopharmacologic treatment. ECT has been reported as an effective treatment for SIB in ASD but only through case reports. The major aim of this research study is to provide prospective research data of the efficacy of ECT in this population.

Specific Aim 1: Clarification, verification, and characterization of the presence of SIB in ASD subjects prior to ECT, through the use of the Self Injury Trauma Scale and daily caregiver assessments of self-injurious behavior.

Specific Aim 2: To measure the efficacy of ECT on SIB by comparing clinical, physical, and psychological signs and symptoms pre and post ECT using the Self-injury Trauma Scale, Repetitive Behavior Scale-Revised, Aberrant Behavior Checklist, ASD Diagnostic Checklist, and the caregiver's daily diary card.

Hypothesis 2: ECT will be an effective treatment for SIB as measured by improvements in the Self-injury Trauma Scale, Repetitive Behavior Scale-Revised, Aberrant Behavior Checklist, and the daily diary card, kept by the caregiver. ECT will not lead to significant changes in the ASD Diagnostic Checklist.

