For this study, all adult individuals presenting to EVMS Psychiatry and Behavioral Sciences will be considered for this clinical treatment study if they have a documented ASD diagnosis by a psychiatrist or psychologist. Participants (N=20) must be over the age of 18, and must have an LAR who can consent to medical treatment and attend all appointments with the participant. Only the participant's LAR may consent to treatment (no participants in this study will be permitted to self-consent). Those individuals considered wards of the state will be considered for the study as long as they meet all inclusion/exclusion criteria and are able to follow through with all steps of the protocol (e.g., guardianship, consent, transportation, etc.). Additionally, the participant must have a present history of self-injurious behavior (SIB) that significantly impacts their quality of life, for which they have tried and failed at least four other treatment methods in the past. SIB is any behavior "which produces injury to the individual's own body." (Tate and Baroff, 1966). All subjects must be medically cleared per the clinical ECT protocol already in place, which includes obtaining an EKG, Chest X-Ray (CXR), Complete Metabolic Panel (CMP), and Complete Blood Count (CBC). Subjects must also obtain a head CT scan. All studies must be less than 6 months old. Additionally, subjects must receive a full clinical psychiatric evaluation with the principal investigators: [name], MD to evaluate for appropriateness for and response to ECT and [name], MD to evaluate for ASD symptoms in subjects prior to, during, and at follow-up.

Study Design

This study design is single subject design over multiple participants. Any patient who is enrolled for ECT with a diagnosis of ASD and SIB that meets inclusion and exclusion criteria will be entered into the study if their guardian/subject provides consent/assent. All ECT procedures will be performed at the SNGH outpatient surgical suite.

Procedure

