ASD Diagnostic Checklist (ADC) was designed after the ADOS, ADI-R, and DSM-V criteria for autism. It is a 25 item instrument, completed by the caregiver, used to assess, (1) qualitative impairment in social interaction, (2) difficulties in communication, and (3) restricted, repetitive, and stereotyped patterns of behavior. It is a tool that will be used as verification that the subject qualifies for an ASD diagnosis in addition to providing the density of ASD symptoms present specific to each patient..

Repetitive Behavior Scale-Revised (RBS-R) is a 43 item instrument completed by caregivers that is rated on a four-point Likert scale ranging from “behavior does not occur” to “behavior occurs and is a severe problem”. The revised scale is specifically intended to assess the variety of RRBs in individuals with ASDs. It is grouped into 5 subscales: 1) stereotyped behavior, 2) self-injurious behavior, 3) compulsive behavior, 4) ritualistic/sameness behavior and 5) restricted behavior. Cronbach’s alpha ranged from 0.78 for the restricted interest subscale to 0.91 for the ritualistic/sameness behavior subscale.¹⁹

Aberrant Behavior Checklist (ABC), is useful for evaluating inappropriate and maladaptive behavior. It is normed from childhood to adulthood and has 58 items rated on a Likert scale. Separate factor analyses result in five-factor subscales: 1) Irritability, Agitation, Crying; 2) Lethargy, Social Withdrawal; 3) Stereotypic Behavior; 4) Hyperactivity, Noncompliance; and 5) Inappropriate Speech^{20,21}. The ABC has had confirmatory and exploratory factor analyses in 1893 children evaluated as part of the Autism Treatment Network which supported the convergent and divergent validity of the ABC as a measure of behavior problems in ASD.²² In practice, the ABC has the option to be completed by a parent, teacher, supervisor, or other guardian/ caregiver. In this study, the ABC will be completed only by a guardian/LAR/ caregiver or by the participant.

Human Subjects Protection

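### As described, the Diary Card lists severity once for both self-injury and aggression, so on days with both behaviours the rating cannot be attributed to self-injury

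*Protocol*

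**What the plan says.** Section IV, Procedure, states that from Visit 1 the guardian or caregiver keeps a Diary Card recording "the number of self-injury episodes per day, the number of aggressive episodes per day, and the perceived severity of episodes that day". The card also has space for medication and, once ECT begins, for side effects. The Measures section describes the SIT, the ADC, the RBS-R and the ABC but not the card, so the protocol gives no severity scale, no anchors and no rule for rating a day with several episodes.

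Section II uses the diary as a measure of SIB in two places. Specific Aim 1 characterises SIB before ECT "through the use of the Self Injury Trauma Scale and daily caregiver assessments of self-injurious behavior". Hypothesis 2 lists the measures whose improvement would show that ECT is effective for SIB and ends with "Aberrant Behavior Checklist, and the daily diary card, kept by the caregiver", without saying which item on the card is meant.

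Two other measures are specific to SIB. The physician-completed SIT "documents the number, type, and severity of unhealed self-injury traumas", and from it "a Number Index, Severity Index, and Estimate of Current Risk can be calculated". For the caregiver-rated RBS-R, the Measures section says: "It is grouped into 5 subscales: 1) stereotyped behavior, 2) self-injurious behavior". In the visit table both are scheduled at Visit 1 and then at Visits 15 to 18.

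**The concern.** A severity rating that follows two separate counts and refers only to episodes naturally reads as covering both behaviours. If caregivers complete it that way, a change in the severity of aggression moves the rating when SIB severity has not changed, and it can offset a real change in SIB severity.

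This matters because of the schedule. The study is declared a single-subject design over multiple participants, so each participant's own series before and during treatment carries much of the comparison. The diary supplies that series, and its severity item is the only severity measure scheduled through the 12 treatments. It is also fixed at data collection: a later analysis plan can choose which item to analyse, but it cannot split a rating recorded once for a mixed day.

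**Working it through.** The protocol gives no figure for diary severity, so there is none to reproduce. The check sets the passages side by side and then uses arithmetic on assumed values.

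**1. What the rating describes, by type of day**

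| Day, from the two counts | What the single rating describes | Usable as SIB severity? |
|---|---|---|
| Self-injury only | SIB | Yes |
| Aggression only | Aggression | No, but identifiable |
| Both | An unknown mixture | No, and not recoverable |
| Neither | No episode | No rating needed |

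**2. When SIB severity is measured** (visit table)

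- SIT and RBS-R: Visit 1 (Week 1), then Visit 15 (Week 7). Neither is scheduled at Visits 2 to 14.
- Diary: cards 1 and 2 before ECT, cards 3 to 6 from the first treatment visit to Visit 15.

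**3. Mixed days with unchanged counts** (assumed: severity 0 to 4, rating is the mean over the day's episodes, 4 self-injury and 4 aggressive episodes both before and during treatment)

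- SIB unchanged at 2, aggression falls from 4 to 2. Before: (4×2 + 4×4)/8 = 3.0. After: (4×2 + 4×2)/8 = 2.0. The rating improves with no change in SIB.
- SIB falls from 3 to 1, aggression rises from 2 to 4. Before: (4×3 + 4×2)/8 = 2.5. After: (4×1 + 4×4)/8 = 2.5. A real improvement in SIB severity does not show. If the caregiver rated the worst episode instead, the rating would rise from 3 to 4.

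Both counts stay at 4 throughout, so they do not reveal either case.

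**4. How the size depends on how often aggression occurs** (assumed: each behaviour's daily severity is independent and uniform on 0, 1, 2, 3; the worst episode is rated; aggression is in play on a share p of days and absent on the rest)

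- Mean of one behaviour: (0 + 1 + 2 + 3)/4 = 1.5.
- Mean of the larger of two: (0×1 + 1×3 + 2×5 + 3×7)/16 = 34/16 = 2.125.
- Mean rating before: 1.5 + 0.625p. If aggression stops and SIB is unchanged, it becomes 1.5.
- Apparent fall: 0.625p/(1.5 + 0.625p).

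| p | Mean before | Apparent fall |
|---|---|---|
| 0 | 1.500 | 0% |
| 0.25 | 1.656 | 9.4% |
| 0.5 | 1.8125 | 17.2% |
| 1 | 2.125 | 29.4% |

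By symmetry, at p = 1 a complete stop of SIB with aggression unchanged also lowers the rating by only 29.4%. In both of these scenarios the separate counts would show what had happened.

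**The case against.** The strongest reply is that the card itself is not shown. The Procedure text is a one-sentence summary and does not say that there is a single or combined rating. A card with a severity field beside each count could be described in the same words. This stands: a reader might infer that the form certainly has one severity box, and the protocol does not establish that. What it establishes is that severity is listed once and tied to neither behaviour.

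Second, the counts are separate. If either behaviour stops altogether, its count goes to 0, and single-behaviour days can be recognised. This also stands. A reader might infer that the diary as a whole cannot separate SIB from aggression; that is too strong, because only mixed days are lost, and only for severity.

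Third, SIB is covered elsewhere by the daily count, the SIT Severity Index and the RBS-R subscale. This limits the harm but does not remove it. The count is not a severity measure, and the two scales are not scheduled during treatment.

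Fourth, the choice of diary variable may be left to a statistical analysis plan that is not shown. This is fair for the analysis, but such a plan cannot recover a rating that was never taken separately, and the loose reference to the whole card stands in the protocol's own hypothesis.

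**Conclusion.** The point holds in a limited form. As the protocol describes the card, the diary severity item is not a measure of SIB on days with both behaviours, and Hypothesis 2 is worded so that improvement in aggression or in a mixed rating could be cited as SIB efficacy. The daily self-injury count and the two SIB-specific scales are sound on this point.

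The size cannot be stated from the protocol. It depends on how often both behaviours occur on the same day, which is not given; aggression is not an entry criterion, and for a participant without it the effect is zero. A reader might take 29% as the expected bias. It is only the upper end of an illustration that assumes a 0 to 3 scale, uniform and independent severities, a worst-episode rule and aggression in play every day. None of these assumptions comes from the protocol.

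The change is worth making because it is nearly free and mixed-day ratings cannot be recovered afterwards. It does not call the whole diary into question.

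**What to change.** - Check the card. If it already has separate severity fields, correct the description in the Procedure section; the card then needs no change.
- Otherwise give it two severity lines, one for self-injury and one for aggression, with self-injury severity scored 0 on days without self-injury. State the scale and how a day with several episodes is rated.
- In Hypothesis 2, replace the reference to the diary card as a whole with the daily self-injury count and the self-injury severity from the card, and report aggression separately.
- For cards already completed, use the severity rating as a SIB measure only on days with self-injury and no aggression, and report how many days this leaves before and during treatment. These days are a selected subset, so the result is supportive only.

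The cost is one extra line on the card, a wording change in Hypothesis 2 and a few more seconds a day for the caregiver. Mixed days already recorded remain unusable for SIB severity.

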Specific aim 3: Monitor and evaluate the side effect profile of ECT in this population of subjects.

Hypothesis 3: ECT will have no additional side effects in this population other than those seen in any psychiatric population receiving ECT.

III. Background, Rationale, and Significance of the Study:

Persons diagnosed with Autism Spectrum Disorder (ASD) are more likely to have a comorbid psychiatric disorder than their neurotypical peers.¹ As many as 11% of children with ASD in the United States have been admitted to a psychiatric hospital by the time they turn 21 years old. Moreover, self-injurious behavior (SIB) is one of the strongest predictors of psychiatric hospitalization among children with ASD aged 5 to 21 years.² Tate and Baroff define SIB as any behavior which “produces injury to the individual’s own body.”³ According to the Self-Injury Trauma Scale, SIB categories include: forceful contact with head or face; forceful contact with other body part; scratching, picking, rubbing skin; biting; eye gouging; ingestion of inedible materials; vomiting or rumination; air swallowing; and hair pulling⁴.

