After receiving medical clearance, or "low risk" to undergo ECT, participants (accompanied by their guardians/ caregiver) will begin to receive ECT treatments. They will receive ECT 3 times a week for 4 weeks, for a total of 12 treatments (Visits 3- 14). All ECT treatments will take place in the Outpatient Surgery and Diagnostic Unit of Sentara Norfolk General, and will be performed by [name] or [name]. All subjects will receive bilateral "brief" ECT, based on the potential risk that self-injurious behavior holds. Participants will be placed under general anesthesia (Etomidate) and after it is determined that the anesthesia is in effect they will be given a primary muscle relaxant (Succinylcholine). Patients will receive one bag of IV NS fluids. An anesthesiologist or nurse anesthetist will hyperventilate the patient to lower their seizure threshold. Two electrodes will be placed bi-temporally. An electric current will pass through the electrodes to the brain through a process of conduction. During initial treatment (Visit 3), the total amount of energy will be titrated until a short seizure is produced, which is called seizure threshold. During subsequent visits (Visits 4-14), the settings will be adjusted to a total energy of 2.5 x seizure threshold, as determined by the ECT provider. Electrical activity in the brain, including seizure quality, duration, and post-ictal suppression of seizure, will be determined by electroencephalogram (EEG). Throughout the procedure, the provider will be monitoring blood pressure, heart rate, and oxygen saturation. While asleep, the participant will be given oxygen through an oxygen mask and a bite block will be placed to protect the teeth and tongue during stimulation. Following the procedure, the patient will recover in the Post Anesthesia Care Unit.

Throughout the course of the treatment, guardians/ caregiver will continue filling out the Diary Card. Once treatment begins, guardians/ caregiver will be asked to also include any side effects of the treatment noted by themselves or the participant. Guardians/ caregiver will turn in and receive new Diary Cards at Visit 3, Visit 6, Visit 9, and Visit 12. After Visit 14, patients will begin to receive maintenance ECT as prescribed by the ECT physician.

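### The Procedure text and the visit table give incompatible timings for Visits 15 and 16, which shifts the first two post-ECT assessments by at least about 3 weeks

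*Protocol*

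**What the plan says.** **Visit timing (Protocol, section IV, Procedure and timeline table).** Acute ECT is given three times a week for four weeks, 12 treatments in all, at Visits 3 to 14. The text then states "Visits 15-18 will occur at 1 month, 2 months, 6 months, and 12 months", counted from the end of acute treatment. In the table, Visits 3 to 14 occupy Weeks 3 to 6, Visit 15 is in Week 7 and Visit 16 in Week 11. Visits 17 and 18 are labelled 6 and 12 months with no origin given. All four visits list the same four instruments: ADC, RBS-R, ABC and the Self-Injury Trauma Scale.

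**Diary cards.** From Visit 1 the caregiver records "the number of self-injury episodes per day, the number of aggressive episodes per day, and the perceived severity of episodes that day". In addition, "The Diary Card also has space to record the medication taken by the participant every day". Side effects are added later: "Once treatment begins, guardians/ caregiver will be asked to also include any side effects of the treatment noted by themselves or the participant". In the table, Card 6 is issued at Visit 12 and returned at Visit 15, when Cards 7 to 10 are issued. Those four are returned at Visit 16. The diary column is empty for Visits 17 and 18.

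**Continuing exposure and Aim 3.** "After Visit 14, patients will begin to receive maintenance ECT as prescribed by the ECT physician"; no end is stated. Specific Aim 3 is to "Monitor and evaluate the side effect profile of ECT in this population of subjects".

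**The concern.** Text and table describe the same visits and cannot both be followed. Aim 2 compares the scales before and after ECT, and Visits 15 and 16 supply the first two post-ECT scores. One reading takes the first of these just after the last acute treatment, the other about a month later, by which time maintenance ECT may also have been given. If staff follow the text for some participants and the table for others, the same visit label will cover different times since treatment. With 20 participants in a single-subject design, that cannot be averaged away.

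The timing also decides whether the diary, another Aim 2 measure, runs without a break through the weeks just after acute ECT. Missed daily entries cannot be rebuilt later.

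For Aim 3 the stake is smaller. Without an earlier daily record of complaints such as headache or nausea, the diary alone cannot separate new or worse complaints from existing ones.

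**Working it through.** **Inputs.** Acute ECT: 12 treatments at 3 per week (Procedure). ECT starts in Week 3; Visit 15 is in Week 7 and Visit 16 in Week 11 (table). Visits 15 and 16 are at 1 and 2 months after acute ECT (text). Assumption: a month is 4 weeks, or 365.25 / 12 / 7 = 4.35 weeks.

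**Step 1: end of acute ECT.** 12 / 3 = 4 weeks, so Weeks 3 to 6. Text and table agree here.

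**Step 2: visit times under each reading.** Table: week number minus 6. Text: months times 4 or 4.35; adding 6 gives the study week.

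| | Table, weeks after acute ECT | Text, weeks after acute ECT | Text, study week | Shift |
|---|---|---|---|---|
| Visit 15 | 7 − 6 = 1 | 4 to 4.35 | 10 to 10.3 | 3.0 to 3.3 weeks |
| Visit 16 | 11 − 6 = 5 | 8 to 8.7 | 14 to 14.7 | 3.0 to 3.7 weeks |

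The text's 1 and 2 months therefore do not reproduce from the table. If a visit may fall on any day of its table week, the upper ends of the shift rise to 4.35 − 0 = 4.35 and 8.7 − 4 = 4.7 weeks. The lower end stays at 3.

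**Step 3: where the mismatch may come from.** Counted from the start of ECT, Week 7 is 7 − 3 = 4 weeks and Week 11 is 11 − 3 = 8 weeks, which would fit 1 and 2 months. The text, however, names the end of acute ECT as its origin. The spacing between the two visits is about a month on both readings (11 − 7 = 4 weeks), so the conflict is one of origin.

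**Step 4: diary coverage.** No card length is stated, so it is inferred. Cards 1 to 6 run from Week 1 to Week 7, six cards in six weeks; Cards 7 to 10 run from Week 7 to Week 11, four cards in four weeks. That is about one week per card.

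- Table timing: Card 6 covers Week 6 and Visit 15 follows in Week 7, so there is no gap.
- Text timing: Card 6 covers Week 6, and the next cards come about 4 weeks after acute ECT. Weeks 7 to 10, about four weeks, have no card.

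**Step 5: side-effect record.** Cards 1 and 2 are both back by Visit 3, when ECT starts. The side-effect request begins with treatment, so neither card is described as carrying it. After Visit 16 the table lists no card. On the table timing, 12 months after acute ECT is Week 6 + 52.2 = 58.2, which leaves 58.2 − 11 = about 47 weeks. On the text timing, 12 − 2 = 10 months remain.

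**The case against.** The timing contradiction is hard to contest, but the diary and side-effect points can be challenged.

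- **The diary gap is conditional.** It needs the text timing and a one-week card, and a card could be kept longer. This stands, so the four weeks are a consequence under stated assumptions.
- **The diary card is not shown.** Its content is inferred from the Procedure text. Side effects of ECT also cannot precede ECT, so the gap is only a missing baseline for the same complaints. The pre-ECT physical examination and the Visit 2 psychiatric evaluation may note some of them, though not as daily caregiver entries. This stands and narrows the point.
- **A reader might infer that safety goes unrecorded in follow-up.** The documents do not support that. Investigators have access to the ECT physician's notes (Procedure), patients and caregivers are questioned about psychological symptoms at every treatment (Protection against Risks), and investigators review side effects and report serious events (Reporting of Serious Adverse Events). One investigator also sees participants "to evaluate for ASD symptoms in subjects prior to, during, and at follow-up". None of these is a uniform side-effect question at Visits 17 and 18.
- **The text on post-treatment appointments could mean that diary cards are issued at all four of them.** The table lists none at Visits 17 and 18. This is a further ambiguity for the same reconciliation to settle.
- **A reader might infer that the timing conflict distorts a memory assessment**, because Risks to the Subject describes recovery over weeks to months. That period runs from completion of treatment, whereas maintenance ECT follows Visit 14, and no visit lists a memory measure.
- **A reader might fault Hypothesis 3**, "ECT will have no additional side effects in this population other than those seen in any psychiatric population receiving ECT", for lacking a decision rule or confidence limits. Those commonly belong in a statistical analysis plan, which is not shown, so no finding is made.

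**Conclusion.** The contradiction stands on the protocol's own wording. Visits 15 and 16 fall about 1 and 5 weeks after acute ECT by the table and about 4 and 8 to 9 weeks by the text, a shift of at least about 3 weeks each. It rests only on ECT ending in Week 6, which both sources support, and on a month of 4 to 4.35 weeks. It affects the Aim 2 scales directly. It affects the diary to the extent of about four uncovered weeks if the text timing is followed and a card lasts a week. The documents do not show which timing was intended; the match with the start of ECT is a possible explanation only.

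The Aim 3 points are secondary. The diary as described gives no daily pre-ECT record of the complaints later reported as side effects, and no side-effect item is listed at Visits 17 and 18 while maintenance ECT may continue. These are improvements worth making. They are not evidence that side effects go uncaptured.

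**What to change.** 1. Reconcile the Procedure text and the timeline table. State one origin and one timing for Visits 15 to 18, including the origin of the 6- and 12-month rows, and say at which of these visits diary cards are issued.
2. If the text timing is kept, issue diary cards to cover the weeks between Visit 14 and Visit 15: about four copies of the existing card, if one lasts a week.
3. As a secondary change for Aim 3, put the symptom line used during ECT on Diary Cards 1 and 2, and add a question on side effects since the last visit to the To-Do entries for Visits 17 and 18.

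The cost is one text and table correction, possibly a few extra cards, one line on two cards and one question at two existing visits. No visit is added. The downside is slightly more writing for caregivers.
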